## Specific Objectives

The primary outcome measure of this study is recovery of peripheral nerve function in type 2 diabetic Veterans. Secondary outcome measures of exercise intervention include changes in aerobic capacity, peak torque, pain perception and health care use. Exercise-induced rehabilitation of diabetic veterans with neuropathy is an overdue concept that remains poorly studied and merits a prospective clinical investigation. Edward Hines, Jr. VA hospital will serve as a readily available resource for completing these studies.

The hypothesis of this study will be tested with the following two *Specific Objectives*:

- a. We will determine the effect of aerobic training, isokinetic strength training, or the combination of aerobic plus isokinetic strength training compared with non-exercise intervention on recovery of peripheral nerve function in age-matched type 2 diabetic Veterans with neuropathy.
  - i. Type 2 diabetic Veterans with established staged length-dependent sensorimotor polyneuropathy will be randomized to a 12 week program of exercise (aerobic, isokinetic, or the combination) or control (non-exercise) intervention. Isokinetic strength promoting leg extensions will be performed on a calibrated Biodex System 3 dynamometer. Aerobic exercise will consist of walking. Sustainability of intervention will be evaluated by repeated testing at 24 weeks. All subject groups will participate in identical biweekly diabetes-related Health Promotion Educational seminars designed to normalize participation.
  - ii. The effects of aerobic training, isokinetic strength training, or the combination of aerobic and isokinetic strength training compared with non-exercise intervention on recovery of peripheral nerve function will be statistically determined from baseline and follow-up testing using a battery of qualitative and quantitative assessments that include clinical history, physical and neurological examination, electrodiagnostic primary outcome measures, Quantitative Sensory Testing, completion of Total Neuropathy Score, visual analogue pain scale, quality of life (SF-36V Health Survey), peak torque (Biodex), peak oxygen uptake (incremental symptom-limited treadmill test) and everyday physical activity (Actical accelerometer physical activity counts).

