**Medical Management:** We realize that subjects within the exercise intervention groups may need to have their diabetic medications adjusted. We hypothesize that exercise intervention will improve peripheral nerve function by enhancing tissue oxygenation in addition to improved blood glucose control. Because physical activity lowers insulin resistance, hypoglycemia may occur during treadmill testing or exercise interventions and up to 48 h afterwards. Blood glucose will be monitored before and after each exercise training session. Subjects will not begin treadmill testing or exercise interventions until their blood glucose levels are between 100 and 250 mg/dL. All enrolled subjects will be asked to perform and record daily blood glucose during the study. Forms for recording the daily blood glucose level will be given to the subjects. If needed, the equipment required for blood glucose measurement will be provided. Blood glucose will be measured each time subjects are seen in the Physical Performance Research Laboratory (see below). Adjusting a subject's medication to better manage blood glucose control is a priority health care issue and not contra-indicated. As previously conducted, immediate management

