concerns are addressed by our collaborator endocrinologist [name]. The subject's primary care physician is consulted and kept informed to oversee comprehensive clinical management of the study subjects' diabetes throughout the duration of this project. **A staff cardiologist ([name], Co-Investigator, Staff Physician and Director of Cardiographics) will review all treadmill exercise test electrocardiograms (ECG).** In the event the treadmill ECG is positive, patients will be referred for appropriate follow-up. If the patient has coronary artery disease, unstable angina or other findings that would make it unsafe for he/she to engage in an exercise program, they will be withdrawn from the study. If needed, a cardiologist at the Hines VA Hospital will interpret these tests immediately; a cardiologist is readily available to the Physical Performance Research Laboratory. The subjects' primary care physician will be aware that their patients are enrolled in the study. A summary of the subject's response to each exercise training session and incremental treadmill test will be entered in the subjects' medical record (via computer). When requested more detailed summaries will be provided to the subjects' physician. In the event that baseline, 12 or 24 week follow-up assessment demonstrates ischemic disease, study staff will work closely with the Hines Cardiology Service and the patient's primary care physician. Drs. [name] and [name] will not be blinded to this study and will not participate in the data analysis and interpretation of the proposed clinical trial. **Foot problems constitute the primary cause of hospitalization of individuals with diabetes.** All subjects will undergo a detailed foot exam during pre-screening prior to entry into this study as part of our enrollment process. All enrolled subjects will undergo routine foot exams prior to intervention regardless of group assignment and are strongly encouraged to perform daily self foot-exams as part of their educational awareness training. To encourage proper foot care, the subject, a family member, or a caregiver will perform regular foot examinations which includes checking the dorsal and plantar surfaces and between the toes for red or warm spots, swelling, pain, breaks in the skin and blisters. All enrolled subjects will be required to wear well-fitting athletic shoes. Foot examinations will also be performed during intervention training; three times per week during the exercise portion of the protocol. All Physical Performance Research Laboratory staff have attended the podiatry foot clinic and received training in foot examination by the podiatrists at Hines and mechanisms for referral. At the earliest sign of foot problems, the subject will be referred to the Hines Podiatry Section for follow-up.

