**Exercise Interventions:** Aerobic exercise will consist of treadmill walking. Isokinetic strength promoting leg extensions will be performed on a calibrated Biodex System 3 dynamometer. The use of Biodex machine is proposed as an experimental means of determining the impact isokinetic strength training has on recovery of peripheral nerve function in diabetic neuropathic veteran. Demonstrating effect with isokinetic strength training, or in combination with aerobic training, will be used as a strong rationale for implementing interventions of this type into clinical rehabilitative practice. **Subjects randomized to the combined aerobic plus isokinetic strength training** will receive isokinetic strength training followed by aerobic treadmill training so that maximal benefits can be gained from the strength program. Patients will be allowed to rest 15-30 minutes between strength and aerobic training with each session ending with a 10 minute cool-down period. Based on prior experience with exercise intervention studies, we anticipate an 80% retention rate within this intervention group. Our sample size for this group includes a 20% attrition rate to compensate for subjects unable or unwilling to complete the 24-week intervention program. Sustainability of interventions will be evaluated by repeated testing at 24 weeks. **All subject groups will participate in identical biweekly diabetes-related Health Promotion Educational seminars designed to normalize participation.**

Subjects randomized to aerobic, isokinetic, or the combination of aerobic plus isokinetic exercise group will be trained in the Physical Performance Laboratory three times weekly. A 10 minute warm-up consisting of stretching

and flexibility exercises will precede all training sessions. Exercised training duration and intensity will progress as listed in the following table:

Strength Training (maximal isokinetic muscle action; velocity of $90^{\circ} \cdot s^{-1}$ )		Aerobic Training (Walking)
Weeks 1-2	3 sets, 10 repetitions, 1 min rest between sets	25 min at 60-70% $VO_2$ peak; 5 min 71-80% $VO_2$ peak
Weeks 3-4	4 sets, 10 repetitions, 1 min rest between sets	25 min at 60-70% $VO_2$ peak; 10 min 71-80% $VO_2$ peak
Weeks 5-6	5 sets, 10 repetitions, 1 min rest between sets	25 min at 60-70% $VO_2$ peak; 15 min 71-80% $VO_2$ peak
Weeks 7-8	6 sets, 10 repetitions, 1 min rest between sets	25 min at 60-70% $VO_2$ peak; 17 min 71-80% $VO_2$ peak; 3 min 81-90% $VO_2$ peak

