**Whereas electrodiagnostic findings constitute the primary outcome measure of this study (see below), secondary outcome measures of exercise intervention include** changes in aerobic capacity, peak torque, quality of life measures including pain perception and health care use (medications (type and dosage), number of diabetes-related clinical visits, number of diabetes-related hospital admissions and length of stay, number of diabetes-related ER visits). Changes in primary outcome findings will be statistically compared (correlations) with the various secondary measures to determine effect of exercise intervention on quality of life. Our previous experience suggests that improved peripheral nerve function significantly enhances quality of life measures in diabetic subjects. Identifying a correlative statistical relationship between primary and secondary outcome measures, as proposed, will be used as a strong rationale for supporting exercise intervention in the management of diabetic neuropathy in affected Veterans. The clinical history and secondary neurologic findings will be quantitated using previously established and validated measures. Relative neurologic deficits will be quantitated using the Total Neuropathy Score, TNS and NSS. Disability will be graded on a scale of 0 to 5 using a modified Rankin Scale. The specifics of the scoring are shown in Appendix A & B. Health related quality of life will be measured using a SF-36V Health Survey. Pain perception will be evaluated using a validated analogue visual pain scale. Level of chronic physical activity will be quantitated using activity counts from Actical accelerometers. Biceps, triceps, brachioradialis, patellar and Achilles' phasic myotatic ("deep tendon") reflexes will be tested bilaterally in every patient. Diminished reflexes will only be considered abnormal if asymmetric or if different from a previous examination. The subject will be scored 1 point for each diminished reflex and 2 points for an absent reflex for a maximum possible score of 20. This scoring is similar for both the TNS and NSS scores. Vibration, proprioception, pinprick and light touch will be evaluated in every subject. For the NSS, each modality will be given a numerical score of 0 to 5 depending on the degree of sensory deficit. The scores will be added so that a patient could have a maximum score of 20. This is similar to the Sensory Function Score in the TNS. The TNS scale is, however, skewed somewhat distally but also records changes in temperature sensation. Sensory perception will also be assessed by the ability to feel 1 and 10-gram filaments applied to the left large toe and index finger (Sensory Testing Systems, Dallas).

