Data collected at 12 weeks will be analyzed, using baseline measurements as a covariate. This will be repeated with the data that are collected at 24 weeks. In both analyses, primary interest will be in the combined aerobic training plus isokinetic strength training interaction. We hypothesize that patients with the combined exercise program will experience the best outcome. Although data will be collected across three time periods (baseline, 12 weeks, and 24 weeks), we have chosen to not employ a repeated measures design. There are two reasons for this: (i) the proposed study is designed to determine the combined influence of aerobic and isokinetic training on recovery of peripheral nerve function, which we believe is best achieved with a factorial design and (ii) our previous experience identified baseline differences among groups of diabetic neuropathy subjects. These group differences will go uncontrolled using a repeated measures design, but can be controlled statistically with analysis of covariance. Therefore, the aerobic plus isokinetic strength training interaction for our primary electrodiagnostic measures will be observed at 12 weeks, controlling for baseline values. This will be done again for the data collected at 24 weeks. A 2 x 2 factorial analysis of covariance also will be conducted with secondary outcome measures such as changes in aerobic capacity, peak torque, pain perception and health care use. Again, data collected both at 12 and 24 weeks will be analyzed using baseline measurements as a covariate. These analyses will allow us to observe the extent to which the secondary measures dovetail with the primary electrodiagnostic measures. In addition, primary outcomes will be correlated with secondary outcomes in order to assess the association of recovery of peripheral nerve function and quality of life. Partial correlation coefficients will be computed at 12 weeks, controlling for baseline values. This will be repeated for the data collected at 24 weeks.

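### Health care use cannot separate study-triggered care from other need for care when exercise arms are compared with control, because staff foot and glucose checks at training occur only in the exercise arms

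*Combined protocol and SAP*

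**What the plan says.** Specific Objective A, part ii, lists "health care use (medications (type and dosage" among the secondary outcomes, together with the "number of diabetes-related clinical visits, number of diabetes-related hospital admissions and length of stay, number of diabetes-related ER visits". The Statistical Analysis Plan applies the 2 x 2 factorial ANCOVA to "secondary outcome measures such as changes in aerobic capacity, peak torque, pain perception and health care use", at 12 and again at 24 weeks, with the baseline value as covariate.

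The follow-up schedule differs by arm:

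- **Exercise arms only.** Participants are "will be trained in the Physical Performance Laboratory three times weekly" (Exercise Interventions). Under Medical Management, "Blood glucose will be monitored before and after each exercise training session", and "Foot examinations will also be performed during intervention training; three times per week during the exercise portion of the protocol". The same section says that a summary of each session goes into the medical record, and that participants in the exercise groups may need changes to their diabetes medication.
- **All arms.** Everyone records home glucose daily (Medical Management). Everyone has 12 nurse-led visits over 24 weeks with glucose review (Conventional Care). All have a routine foot examination before intervention and are encouraged to examine their own feet.
- **Referral rule.** "At the earliest sign of foot problems, the subject will be referred to the Hines Podiatry Section for follow-up". This is written for any participant.

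The documents do not define a diabetes-related clinical visit. They do not name its data source or counting window, or say whether study sessions and the care they trigger are counted.

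**The concern.** A between-arm comparison of visits or medication changes reads as a comparison of need only if a given problem has a similar chance of becoming a counted event in each arm. Here a small foot lesion in an exercise participant is likely to meet a trained examiner within days and be referred. In a control participant it depends on self-examination or on being raised at a nurse visit. Glucose readings are also seen by staff far more often in the exercise arms during training.

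The imbalance begins after randomisation, so a baseline covariate cannot remove it. An apparent rise in visits or dose changes with exercise could be a detection effect. A later fall could partly reflect earlier detection. Either could be reported as an effect of exercise on need for care. The same data also feed the planned correlations with the electrodiagnostic outcomes, which adjust only for baseline.

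**Working it through.** **Inputs from the documents.** Training takes place three times a week. Its length is 12 weeks, from "randomized to a 12 week program of exercise (aerobic, isokinetic, or the combination) or control (non-exercise) intervention" in Specific Objectives and from the training table, which ends at week 12. All arms have 12 nurse visits over 24 weeks. The three test batteries are common to all arms and are left out.

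**Check of the stated figure.** One visit every two weeks for 24 weeks gives 24 / 2 = 12, as stated. Six of these fall in weeks 1-12.

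**Contacts per participant.**

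| | Control | Each exercise arm |
|---|---|---|
| Scheduled contacts, weeks 1-12 | 6 | 6 + 3 x 12 = 42 (7:1) |
| Scheduled contacts, weeks 1-24 | 12 | 12 + 36 = 48 (4:1) |
| Staff glucose checks at these contacts, weeks 1-12 | 6 | 6 + 2 x 36 = 78 |
| Staff foot examinations at training | 0 | 36 |

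All the extra contacts fall in weeks 1-12. Weeks 13-24 have 6 nurse visits in every arm.

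**Effect on the planned contrasts.** Suppose the training schedule adds k counted events per exercise participant and there is no true effect. The cells (control, isokinetic, aerobic, combined) then receive 0, k, k, k.

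- Each main effect: (k + k)/2 - (0 + k)/2 = k/2.
- Interaction: k - k - k + 0 = -k.

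If sessions themselves were counted as visits, k = 36, giving main effects of +18 and an interaction of -36. Leaving scheduled sessions out removes that part. Referrals and medication changes prompted by the checks would remain.

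**Illustration of the remaining part. The rates are assumed, not taken from the documents.** Visits are Poisson, with 20 participants per group, no true effect, and t-tests on contrasts without a baseline covariate at two-sided 0.05. Extra referrals are 0.01, 0.02 or 0.05 per session, so k = 36 x 0.01 = 0.36, 36 x 0.02 = 0.72 or 36 x 0.05 = 1.8.

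| Background visits per 12 weeks | False-positive rate, interaction (k = 0.36 / 0.72 / 1.8) | False-positive rate, pooled exercise vs control |
|---|---|---|
| 1 | 11% / 25% / 75% | 22% / 63% / 100% |
| 2 | 8% / 17% / 59% | 14% / 41% / 98% |
| 4 | 7% / 12% / 41% | 9% / 25% / 87% |

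With k = 0 the simulated rates were about 5%. More variable visit counts than Poisson would lower the inflated rates. The table shows that the answer depends on a referral rate that the plan gives no means of measuring.

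**The case against.** A reader might infer that the outcome measures surveillance rather than need. The documents do not support that, for these reasons.

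- **Contacts are not events.** The 7:1 ratio counts contacts. The documents do not say that sessions count as visits, and they give no referral rate. Ordinary diabetes visits also dilute any effect. As an assumed example, take 2 routine visits and 0.2 referable findings per participant, with 95% detected in exercise arms and 30% to 70% in control. Then (2 + 0.19)/(2 + 0.06) = 1.06 and (2 + 0.19)/(2 + 0.14) = 1.02.
- **Control participants are watched too.** Daily home glucose and 12 nurse visits with glucose review apply to everyone. The collaborating endocrinologist is not restricted to the exercise arms.
- **Medication change may be a real effect.** Medical Management links activity to lower insulin resistance, so a dose change is not simply a detection artefact.
- **Admissions, length of stay and ER visits are not scheduled by the protocol.** Any bias there is at most indirect.
- **Removing session-triggered events creates the opposite bias.** With the same assumed detection rates, if all 95% were found at sessions and deleted, 5% would remain against 30% to 70% in control. That is a ratio of 0.17 to 0.07 in favour of exercise.

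All of this stands, and it limits both the claim and the remedy. It does not supply the missing rule. The shared glucose monitoring narrows the glucose gap but leaves the gap in staff foot examinations at training.

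**Conclusion.** The point holds in a limited form. As planned, the control-versus-exercise comparison of diabetes-related visits and medication changes, and the factorial contrasts that use the control cell, cannot separate study-triggered care from other need for care. Baseline adjustment does not repair this.

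The scheduled imbalance is firm: 42 contacts against 6 by week 12, and 36 staff foot examinations at training against 0. The resulting bias is not known, and the false-positive rates above rest on assumed inputs. Comparisons among the three exercise arms are balanced in session frequency. The primary electrodiagnostic outcomes are not affected by this point. A diminished need for medical care appears in the paragraph on relevance to VA patient care as an expectation; a reader might take it for a stated objective, but the hypothesis and objectives do not list it.

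The counts assume 12 weeks of training. The Exercise Interventions paragraph on retention also describes the intervention programme as lasting 24 weeks, and the two must be reconciled.

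**What to change.** In the secondary-outcome text of Specific Objective A, part ii, and in the Statistical Analysis Plan:

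1. State that scheduled training, education and test visits are not counted as diabetes-related clinical visits.
2. Record prospectively, in all arms, the trigger of each visit and medication change (study session or check, or other) and the direction of each medication change.
3. Report health care use with and without study-triggered events, tabulated by arm. Do not make the exclusion the main analysis, because it would remove mainly exercise-arm events.
4. Report weeks 1-12 and weeks 13-24 separately, once the 12-week and 24-week descriptions of the programme have been reconciled.
5. State that an exercise-versus-control difference in visits or medication will not be read as changed need for care unless it is consistent across these analyses.

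The cost is one extra field on the form and more tabulation. The field has to be in place from the start, because triggers are hard to reconstruct afterwards. The safety examinations stay as they are.

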**Sample Size Estimate:** The requisite sample size for the proposed study has been based upon the primary outcome measure endpoints of conduction velocity and amplitude. In our preliminary studies (see Table 2), we present data from peroneal nerve conduction velocity and amplitude for sedentary and aerobic (PoleStriding) exercise study groups. We use this information for the proposed study. However, we have not conducted strength training studies and, as such, have had to estimate values that we believe are realistic outcomes. The table below is an estimate of the conduction velocity findings for the proposed study.

		Isokinetic Strength Training	
		No	Yes
Aerobic Training	No	38 m/s	39 m/s
	Yes	39 m/s	43 m/s

Using these estimates we have computed that the effect size for the aerobic plus isokinetic strength training interaction is 0.36. From this, computations indicate that 17 subjects per group will provide 80% power with analysis of covariance to detect an effect size of that magnitude using a 0.05 alpha level. In terms of conduction amplitude, the following table is an estimate of the findings for the proposed study. Again, data from our preliminary studies are incorporated.

		Isokinetic Strength Training	
		No	Yes
Aerobic Training	No	1.9 mV	1.9 mV
	Yes	2.4 mV	4 mV

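### The plan uses correlations between nerve and secondary outcomes to determine the effect of exercise on quality of life, but such a correlation contains no comparison between arms and cannot estimate that effect

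*Combined protocol and SAP*

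**What the plan says.** Two places describe the same correlations and give them different jobs.

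- **Research Design and Methods, Specific Objective A, part ii (paragraph on secondary outcome measures).** Changes in the primary findings are to be "statistically compared (correlations) with the various secondary measures to determine effect of exercise intervention on quality of life". The use of the result follows: "Identifying a correlative statistical relationship between primary and secondary outcome measures, as proposed, will be used as a strong rationale for supporting exercise intervention".
- **Statistical Analysis Plan.** Here "primary outcomes will be correlated with secondary outcomes in order to assess the association of recovery of peripheral nerve function and quality of life". The method is one sentence: "Partial correlation coefficients will be computed at 12 weeks, controlling for baseline values". It is repeated for the 24-week data. No arm or factor term, within-arm correlation or mediation model is mentioned.

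The Statistical Analysis Plan also applies the 2 x 2 factorial analysis of covariance (ANCOVA), with the baseline value as covariate, to "secondary outcome measures such as changes in aerobic capacity, peak torque, pain perception and health care use". The SF-36V is not named there. The protocol's description of the SF-36V nevertheless treats it as critical for judging whether exercise meaningfully improves a patient's perceived health.

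**The concern.** An exercise effect on quality of life is a difference between randomised arms. A correlation between two outcomes measured after randomisation compares no arms, so it does not estimate that difference however it turns out. Two things can go wrong.

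1. **Exercise does nothing.** Patients with better nerve function may also feel better, for reasons unrelated to the intervention. The correlation is then real, but it says nothing about exercise.
2. **Exercise shifts both outcomes by separate routes.** If arm is not adjusted for, the differences between arm means produce a correlation even when nerve recovery and quality of life are unrelated within every arm.

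The protocol intends to cite the correlation in support of exercise as a treatment, so either mechanism could supply evidence that the analysis cannot give.

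**Working it through.** The documents give no numerical figure for the correlations. The sample size calculation is used only to recover a planning SD.

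**Inputs from Sample Size Estimate.** Velocity means: control 38, strength 39, aerobic 39, combined 43 m/s, with interaction effect size f = 0.36 and 17 per group for 80% power. Amplitude means: 1.9, 1.9, 2.4, 4 mV, with f = 0.25. The plan expects 20 completers per group (80 in all) from 25 randomised.

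**Reproducing the plan's figure.** Noncentral F, 1 numerator df, noncentrality f² × N, one covariate: f = 0.36 needs 16 per group, and 17 gives 83% power. The stated 17 is reproduced to within one patient per group.

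**Back-solving the SD.** The section states no SD. With f = |interaction contrast| / 4 / SD:
- Velocity: contrast 43 − 39 − 39 + 38 = 3, so SD = 0.75 / 0.36 = 2.083 m/s.
- Amplitude: contrast 4 − 1.9 − 2.4 + 1.9 = 1.6, so SD = 0.4 / 0.25 = 1.6 mV.

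Both are treated as within-arm, baseline-adjusted SDs.

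**Share of variance between arms.**
- Velocity: deviations from 39.75 are −1.75, −0.75, −0.75, 3.25; mean square 14.75 / 4 = 3.6875; share 3.6875 / (3.6875 + 4.340) = 46%.
- Amplitude: mean square 2.97 / 4 = 0.7425; share 0.7425 / (0.7425 + 2.56) = 22.5%.

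**Mechanism 1, exercise does nothing (assumed within-patient correlation 0.2 to 0.3).** Fisher z, n = 80, two baselines partialled out, standard error 1/√75. For r = 0.2: 0.2027 × 8.660 = 1.756, significant in about 42% of trials. For r = 0.3: 0.3095 × 8.660 = 2.680, about 76%.

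**Mechanism 2, arm means only.** Set the within-arm correlation to zero. Let d be the combined-versus-control difference in quality of life in SD units (assumed; the documents give none). Then

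r = mean(μx μy) / √[(between-arm + within-arm variance of x) × (between-arm variance of y + 1)],

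where μx and μy are deviations of the arm means.

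- Velocity, quality of life following the velocity pattern, d = 1: mean product 3.6875 / 5 = 0.7375; between-arm variance of y 3.6875 / 25 = 0.1475; r = 0.7375 / √(8.028 × 1.1475) = 0.24.
- Velocity, equal benefit in all exercise arms, d = 1: mean product 0.4375; between-arm variance of y 0.1875; r = 0.4375 / √(8.028 × 1.1875) = 0.14.

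Percentage of simulated trials with a significant partial correlation (two-sided 5%, both baselines partialled out, 20 per group, 2,000 runs per setting, assumed baseline slope 0.7):

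| Setting | d = 0 | 0.2 | 0.5 | 0.8 | 1.0 |
|---|---|---|---|---|---|
| Velocity, same pattern | 4 | 8 | 19 | 44 | 60 |
| Velocity, equal benefit | 5 | 6 | 10 | 18 | 23 |
| Amplitude, same pattern | 6 | 7 | 13 | 24 | 34 |
| Amplitude, equal benefit | 6 | 6 | 6 | 8 | 12 |

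With 25 per group, velocity with the same pattern runs from 8% at d = 0.2 to 71% at d = 1.0. Adding three arm indicators (20 per group) returns rejection to 4% to 6% in every setting, with mean r about 0.00.

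**The case against.** **The randomised comparison is largely there.** A reader might infer that the correlation is the plan's only route to an exercise effect on quality of life. The documents do not support that. The ANCOVA list is introduced as examples. It names pain perception and health care use, which the protocol itself groups under quality-of-life measures. Naming the SF-36V is therefore a clarification. This point stands, and it limits the consequence.

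**The Statistical Analysis Plan is more modest.** It speaks of association, and nowhere says that nerve recovery causes better quality of life. That is true, but the protocol paragraph still assigns the correlation the larger job, so the two passages conflict.

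**Pooling over arms is read from silence.** The plan never uses the word. Baseline is simply the only control named. This also stands; the point is that no arm term is specified.

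**The rejection rates are not plain false-positive rates.** If exercise shifts both outcomes, their overall association is truly non-zero, and detecting it is correct for an aim of describing association. The rates are errors only against a null of no within-arm relation, which the plan does not state. Adjusting for arm also changes the question, because it removes exercise-induced variation that the investigators may want to see. This stands, and it argues for reporting both versions.

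**The largest figures need favourable assumptions.** Letting quality of life follow the velocity pattern exactly makes the arm means collinear, which maximises r for a given between-arm variance. Larger shifts than 1 SD would give higher rates, but nothing in the documents supports them.

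**Conclusion.** The point holds in a limited form. The correlation cannot determine an effect of exercise on quality of life, because it contains no comparison between arms. That conclusion needs no numerical assumption. It makes the protocol's stated use of the correlation unsupported and inconsistent with the aim in the Statistical Analysis Plan.

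The size of the arm-induced part is conditional. It rests on the back-solved SDs, zero within-arm correlation, 80 subjects and an assumed quality-of-life shift of 0.2 to 1.0 SD. On those terms the unadjusted velocity correlation is significant in about 8% to 60% of trials under the matching pattern and about 6% to 23% under equal benefit. For amplitude the range is about 6% to 34% across both patterns. With no shift in quality of life there is no inflation.

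The primary analysis and the sample size are not affected.

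**What to change.** 1. Reword the secondary-outcomes paragraph under Specific Objective A, part ii, so that the effect of exercise on quality of life is taken from the randomised 2 x 2 ANCOVA, and any rationale for exercise rests on that comparison.
2. Name the SF-36V in the Statistical Analysis Plan among the secondary outcomes for that ANCOVA, with its baseline value as covariate.
3. Describe the correlations in both places as associations only.
4. At 12 and 24 weeks, report the partial correlations twice, side by side: controlling for baseline values as planned, and also adjusted for the aerobic, strength and interaction terms. Label the second set as within-arm associations.

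The cost is wording in the protocol and Statistical Analysis Plan and three degrees of freedom in the adjusted correlations. No new data are needed, and the methods are already in the plan.
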